## **6.3 Secondary Study Endpoints**

- Pharmacodynamic markers of TFP target engagement

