### **7.6.2 Data Collection and Follow-up for Withdrawn Subjects**

Subjects who discontinue from the Treatment Period early will still continue to the Follow-Up Period for 1 week from the last dose of TFP. For any subjects lost to follow-up, attempts will be made by phone to obtain permission to record at least survival data up to the end of study follow-up period.

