## **9.3 Visit 2**

Visit 2 will be Day 11 ( $\pm$  1 day) of the study. The subject will undergo full safety analysis, including a physical examination (including weight, vital signs, blood pressure and neurological exam). Karnofsky performance status will be assessed. Blood work will be performed for a complete blood count (CBC; RBC count, hemoglobin, hematocrit, absolute reticulocyte count, white blood cell count, absolute neutrophil count, and platelet count), serum chemistry panel for hepatic and renal function (blood urea nitrogen, creatinine, bilirubin [total and direct], aspartate aminotransferase [AST], and alanine aminotransferase [ALT]), and

pharmacodynamic marker analysis, if applicable (Appendix J). If the subject is a female, menstrual status will be assessed and a serum pregnancy test will also be performed. Transfusion history will be documented. The subject will be questioned and evaluated for any adverse events. All concomitant therapies will be documented.

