#### **9.5 Visit 4**

Visit 4 will be Day 29 ( $\pm 2$  days) of the study (Follow-up Period). The subject will undergo post-treatment safety assessment including a physical examination and blood work (CBC and chemistry panel). Transfusion history will be documented. The subject will be questioned and evaluated for any adverse events. This visit may be done virtually through a system that can visually assess the subject for neurologic issues. Blood work may be done at a local laboratory.

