## 10 Risks to Subjects

Adverse reactions with TFP include drowsiness, dizziness, skin reactions, rash, dry mouth, insomnia, amenorrhea, fatigue, muscular weakness, anorexia, lactation, blurred vision, and neuromuscular (extrapyramidal) reactions. Details regarding extrapyramidal and other adverse reactions with TFP follow:

- **Neuromuscular (Extrapyramidal) Reactions:** These symptoms are characterized by motor restlessness. They may be of the dystonic type, or they may resemble Parkinsonism (described below).
- **Motor Restlessness:** Symptoms may include agitation or jitteriness and sometimes insomnia. These symptoms often disappear spontaneously.
- **Dystonia (Class Effect):** Symptoms of dystonia, prolonged abnormal contractions of muscle groups, may occur in susceptible individuals during the first few days of treatment. Dystonic symptoms include spasm of the neck muscles, sometimes progressing to tightness of the throat, swallowing difficulty, difficulty breathing, and/or protrusion of the tongue. While these symptoms can occur at low doses, they occur more frequently at higher doses of first generation antipsychotic drugs.
- **Pseudoparkinsonism:** Symptoms may include mask-like facies, drooling, tremors, pill-rolling motion, cogwheel rigidity, and shuffling gait.
- **Tardive Dyskinesia:** Tardive dyskinesia is a rare syndrome characterized by rhythmical involuntary movements of the tongue, face, mouth, or jaw (e.g., protrusion of tongue, puffing of cheeks, puckering of mouth, chewing movements). These symptoms may be accompanied by involuntary movements of extremities. In rare instances, these involuntary movements of the extremities are the only manifestations of tardive dyskinesia. Symptoms may persist for months or years and, while they gradually disappear in some subjects, they may be irreversible in others. The risk appears to be greatest in elderly subjects (especially women) on prolonged, high-dose therapy. There is no known effective treatment for tardive dyskinesia. It has been reported that fine vermicular movements of the tongue may be an early sign of the syndrome and if the medication is stopped at that time the syndrome may not develop.
- **Adverse Reactions Reported with TFP or Other Phenothiazine Derivatives:** Adverse effects with different phenothiazines vary in type, frequency, and mechanism of

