## **15.4 Stopping Rules**

The stopping rules are as follows:

Scenario 1: The occurrence of extrapyramidal symptoms, symptoms suggestive of tardive dyskinesia (including vermicular movements of the tongue), neuroleptic malignant syndrome or any SAE or treatment-emergent AE  $\geq$  Grade 3 felt to be causally related to TFP in a single subject:

- Rule: Treatment will be immediately stopped in that subject and the subject will be discontinued from the study.

Scenario 2: The occurrence of the extrapyramidal symptoms, symptoms suggestive of tardive dyskinesia (including vermicular movements of the tongue), neuroleptic malignant syndrome or the same SAE or treatment-emergent AE  $\geq$  Grade 3 felt to be causally related to TFP in more than 1 subject:

- Rules:
  - a. Treatment will be immediately stopped in those subjects and those subjects will be discontinued from the study.
  - b. If the 2 or more subjects are in Cohort A, the trial will be stopped; no MTD will be declared.
  - c. If the 2 or more subjects are in Cohort B, the study will be stopped, and 1 mg/day will be declared the MTD.

- d. If the 2 or more subjects are in Cohort C, the study will be stopped, and 2 mg/day will be declared the MTD.
- e. If the 2 or more subjects are in Cohort D, the study will be stopped, and 5 mg/day will be declared the MTD.

Scenario 3: Hemoglobin > 12 mg/dL in a subject sustained for more than 7 days (not associated with RBC transfusion)

- Rule: The subject will be considered a complete responder, treatment will be discontinued, and the duration of the effect will be monitored until day 29 after start of treatment.

In addition to the stopping rules, a subject may be discontinued by the investigator at any time for failure to comply with protocol requirements, in the event that the investigator feels that continuation in the study poses a risk to the health of the subject, or if the subject withdraws consent.

The reason for treatment discontinuation must be documented in the subject chart / source records.

The trial will be stopped, as noted above, if more than one subject experiences the occurrence of the extrapyramidal symptoms, symptoms suggestive of tardive dyskinesia, neuroleptic malignant syndrome, the same SAE or treatment-emergent AE  $\geq$  Grade 3 felt to be causally related to TFP at the lowest dose level.

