## 22.1 Appendix A: Study Assessment Schedule

	Screening Period	Treatment Period			Follow-Up
	Screening	Visit 1	Visit 2	Visit 3	Visit 4
	Day -28 to Day -1	Day 1 a (±1d)	Day 11 (±1d)	Day 22 (±2d)	Day 29 (±2d)
Obtain subject informed consent form		-	-	-	-
Assess inclusion/exclusion criteria		-	-	-	-
Obtain medical subject history		-	-	-	-
Record prior treatments and procedures (including transfusion history)		-	-	-	-
Physical examination (including height at 1 st visit only, weight, vital signs, blood pressure and neurological examination)					
Karnofsky performance status (Appendix E)					-
Hematology b,*					
Blood chemistry, hepatic function, kidney function c,*					
Blood for pharmacodynamic disease marker analysis (Appendix J) d	-				-
Menstrual status					-
Pregnancy test e,*				-	-
Transfusion assessment f					
Adverse events	-				

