## 22.10 Appendix J: Blood for Pharmacodynamic Disease Marker Analysis

[Descriptive pilot laboratory investigations will be performed to explore assay feasibility for TFP target engagement. Samples from each subject will be collected to study the pharmacodynamic effect of the drug TFP. Ten mL whole blood will be collected in EDTA (lavender) tubes prior to start of drug administration and at each visit of treatment for a total of 3 samples per subject. The sample will be used to isolate CD34+ cells (precursors for erythrocytes). Total protein and mRNA will be isolated and used to analyze disease markers.

In addition whole blood will be collected in a 3ml EDTA (lavender top) tube to measure the drug amount in serum, to understand the relationship between drug amount and the exploratory physiological impact being monitored. This sample will need to undergo centrifugation prior to shipment of the plasma as per the laboratory manual.]

[These samples should be shipped right after collection by FedEx First Overnight Delivery to:

Attn: [name]  
CAMP4 Therapeutics  
[name]  
[name]  
[name]  
[contact]

The specimens must be labelled with the subject's study ID and study week, as well as date collected.]

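### No pharmacodynamic sample is scheduled when a subject stops TFP early, so subjects stopped between visits, mainly for toxicity, have no end-of-treatment value and some have no on-drug value

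*Combined protocol and SAP*

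**What the plan says.** Section 6.3 lists one secondary endpoint: "Pharmacodynamic markers of TFP target engagement". Appendix J sets the sampling: blood is taken "prior to start of drug administration and at each visit of treatment for a total of 3 samples per subject". It also calls for a smaller tube to measure the amount of drug, so that drug level can be related to the marker. In Appendix A the pharmacodynamic row is ticked at Visits 1, 2 and 3 and carries a dash at Screening and Visit 4. Section 9.5 gives Visit 4 an examination, blood count, chemistry, transfusion history and adverse events. It may be held virtually, with blood work at a local laboratory.

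For early stoppers, section 7.6.2 says: "Subjects who discontinue from the Treatment Period early will still continue to the Follow-Up Period for 1 week from the last dose of TFP". Section 6.1 likewise gives every dosed subject one week of follow-up after stopping. Under Scenario 1 of section 15.4 (extrapyramidal symptoms, a related serious event, or related toxicity of Grade 3 or higher), "Treatment will be immediately stopped in that subject and the subject will be discontinued from the study". No section names an early-termination visit, a marker draw at discontinuation, or the handling of a missing marker sample.

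**The concern.** The sampling plan assumes that every subject reaches Visit 3, yet the protocol has several routes out of treatment before then. The earliest are for toxicity. Section 10 says of dystonia that it "may occur in susceptible individuals during the first few days of treatment", which would be before the first on-drug sample at Day 11.

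With three to six subjects per dose, each missing on-drug value matters to a description by dose. The loss may also be related to what is being measured. Section 3.5 states that side effects of TFP are related to dose and plasma level. Section 3.2.2 reports wide variation in exposure among five healthy men given the same 5 mg dose. Subjects stopped for toxicity could therefore be those with higher exposure. If the drug-level tube is drawn together with the marker blood, an unscheduled stop loses both.

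An analysis rule can still be written after enrolment. A sample that was not drawn near the last dose cannot be recovered.

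**Working it through.** **The plan's own figures.** Marker samples: Visits 1, 2 and 3 give 1 + 1 + 1 = 3 per subject, as Appendix J states. Subjects: at most 4 cohorts × 6 = 24 and at least 1 × 3 = 3, as section 14.1 states. The maximum is 24 × 3 = 72 samples, reached only if nobody stops early.

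**Samples by time of stop.** Visit windows from Appendix A: Visit 2 on Days 10-12, Visit 3 on Days 20-24.

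| Stop | Samples now | On-drug value | Value at the stop | Samples with a draw at the stop |
|---|---|---|---|---|
| Before Visit 2 | 1 (baseline) | none | none | 2 |
| At Visit 2 | 2 | Day 11 | yes | 2 (already covered) |
| Between Visits 2 and 3 | 2 | Day 11 | none | 3 |

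**Could Visit 3 still supply the value?** Follow-up ends 7 days after the last dose. For a last dose on Day 12 or earlier it ends by Day 12 + 7 = Day 19, before the Visit 3 window opens on Day 20. For a last dose on Day 13, the first day of that window is already 7 days later.

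**Could Visit 4 supply it?** Section 3.5.1 gives a half-life of about 12-14 hours. Fraction of drug remaining = 0.5^(hours / half-life).

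- Seven days is 168 h: 168/14 = 12 half-lives, 0.5^12 = 0.024%; 168/12 = 14 half-lives, 0.5^14 = 0.006%.
- For comparison, a completer seen on Day 22, 24 h after the Day 21 dose: 0.5^(24/12) = 25% to 0.5^(24/14) = 30%. Seen on Day 24 (72 h): 1.6% to 2.8%.

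A Visit 4 draw would be a washout sample. This assumes simple exponential decline and a marker that follows drug level; the documents give no time course for the marker.

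**Response stops.** The first scheduled hemoglobin after baseline is at Visit 2. If a single value is enough (6.1), the stop falls at Visit 2, where marker blood is drawn. If the value must be sustained for more than 7 days (15.4, Scenario 3), the earliest day is 10 + 8 = 18 to 12 + 8 = 20, next to the Visit 3 window. Only an unscheduled hemoglobin gives another time. Most response stops therefore coincide with a marker visit.

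**Toxicity stops.** The documents give no toxicity rate, so a constant probability p of Grade 3 or higher toxicity in every cohort is assumed. Let q0 = (1−p)^3 and q1 = 3p(1−p)^2. A cohort has 3 + 3·q1 expected subjects and the trial moves on with probability a = q0 + q1·q0. Expected subjects = (3 + 3·q1)(1 + a + a² + a³); expected toxicities = p × expected subjects.

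Example, p = 0.10: q0 = 0.729, q1 = 0.243, a = 0.906; 3.729 × 3.471 = 12.9 subjects; 0.10 × 12.94 = 1.29 toxicities.

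| p | Expected subjects | Expected toxicities |
|---|---|---|
| 5% | 13.1 | 0.65 |
| 10% | 12.9 | 1.29 |
| 20% | 10.7 | 2.13 |
| 30% | 8.0 | 2.41 |

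These counts are a guide to subjects at risk of a missing value. Some toxicities will be found at Visit 2 or handled by a dose hold. On the other hand, section 15.4 stops subjects for extrapyramidal symptoms of any grade.

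**Variation in exposure (3.2.2).** Peak 0.53 to 3.09 ng/mL: 3.09/0.53 = 5.8-fold. Area under the curve 5.9 to 17.6: 17.6/5.9 = 3.0-fold.

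**The case against.** The strongest reply is that little depends on these samples. Appendix J describes a descriptive pilot of assay feasibility, sections 9.2 to 9.4 make the marker blood conditional, and section 14.2 marks secondary endpoints as not applicable. Section 2 ties a later proof-of-concept trial to tolerability, not to the markers. This stands, and it limits the consequence.

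A second reply is that most stoppers are not lost. Anyone who stops after Visit 2 keeps a Day 11 value, well past the steady state expected at about Day 3 (3.5.1). This also stands: only a stop before Visit 2 leaves no on-drug value.

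A third is that 7.6.2 does not cancel Visit 3. That is literally true, but follow-up ends before Visit 3 for a last dose on Day 12 or earlier, and a later stopper seen at Visit 3 could be days off drug.

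A reader might go further and infer that the missing subjects are those with the strongest target engagement, so that engagement by dose is understated. The documents do not support that. They attribute the antipsychotic action to dopamine blockade in the central nervous system (3.2.1) and the activity relevant to DBA to calmodulin inhibition (3.2.2). Section 10 foresees altering the drug to keep it out of the brain while retaining a possible benefit in DBA. An extrapyramidal stop need not track the marker, and responders mostly stop where marker blood is taken.

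A last reply is practical: subjects may live in any state (7.5) and stops are immediate, so some stop samples will be late. This is why they should not be pooled with the scheduled values.

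**Conclusion.** The gap is real and small. The schedule provides no marker sample at discontinuation and none at Visit 4. A subject stopped before Visit 2 contributes a baseline only, and one stopped between Visits 2 and 3 lacks an end-of-treatment value. Under assumed constant toxicity rates of 5% to 30%, 0.65 to 2.41 subjects in the whole trial would be at risk by the toxicity route.

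The loss may be informative, because side effects are said to follow plasma level, but neither its direction nor its size can be derived from the documents. No shift in a cohort mean should be claimed: none is planned as an analysis, and the link between toxicity and marker change is unknown. No stated figure of the plan changes except the promise of three samples from every subject, which cannot hold for early stoppers. This is a minor point, worth acting on because the data cannot be obtained later and the change costs little.

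**What to change.** 1. In 7.6.2 and Appendix A, draw the next unused planned marker and drug-level sample at the visit where early discontinuation is made or confirmed, as close to the last dose as feasible, and record the time since last dose.
2. List these values by dose with the time since last dose, separately from the scheduled Day 11 and Day 22 values. Report how many subjects have no on-drug sample and why.
3. In Appendix J, change the total of 3 samples per subject to up to 3.
4. Reconcile 6.3, which names the markers as the secondary endpoint, with 14.2, which marks secondary endpoints as not applicable.
5. Reconcile the passages that decide who leaves early. Section 3.5.2 holds dosing for Grade 3 or higher events, whereas 15.4 stops at once when such an event is judged related, and 7.6.1 lists such toxicity as a reason for withdrawal. The hemoglobin criteria in 3.5.2, 6.1, 7.6.1 and 15.4 differ in threshold, duration and unit.

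Cost: a line each in 7.6.2 and Appendix A, a short listing, and no more tubes per subject than planned. Downsides: the time since last dose will vary, and some subjects stopped remotely will still have no sample, since Appendix J requires overnight shipment straight after collection.

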## **8 Study Drug**

### **8.1 Description**

TFP is a commercially-available phenothiazine tranquilizer with potent anti-psychotic, anti-anxiolytic and antiemetic activity.

TFP is commercially available in the United States in a variety of formulations, including the following:

1 mg tablets are lavender, film-coated, round, unscored tablets debossed with 1 on one side of the tablet and GG51 on the other side. They are available as follows: NDC 0781-8028-01, in bottles of 100 tablets.

5 mg tablets are lavender, film-coated, round, unscored tablets debossed with 5 on one side of the tablet and GG55 on the other side. They are available as follows: NDC 0781-8034-01, in bottles of 100 tablets.

## **8.2 Treatment Regimen**

Trifluoperazine will be given orally once daily as 1 mg, 2 mg (two 1mg tablets), 5 mg, or 10 mg (two 5mg tablets). The treatment duration will be up to 21 days (3 weeks).

## **8.3 Method for Assigning Subjects to Treatment Groups (RANDOMIZATION)**

There is no randomization in this study. All subjects who qualify for the study will be enrolled into the study and receive up to 3 weeks of TFP. A unique multi-digit subject identification number will be manually assigned by the site staff to each subject who signs consent.

## **8.4 Preparation and Administration of Study Drug**

The staff in the pharmacy will fill out the following information on the Trifluoperazine Drug Accountability Log upon distribution to the subject:

- Date
- Visit
- Subject Number
- Subject Initials
- Dose
- Number of pills dispensed
- Lot Number

The site personnel will confirm the lot number for TFP and the number of pills dispensed and record this information on the Trifluoperazine Drug Accountability Log and in the pharmacy records.

### **8.5 Subject Compliance Monitoring**

The study team will assess compliance with the study treatment by report at each study visit. The subject may be discontinued by the study PI at any time for non-compliance with the study treatment regimen.

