## **7.6 Early Withdrawal of Subjects**

### **7.6.1 When and How to Withdraw Subjects**

The following reasons are considered sufficient for withdrawing a subject from the study drug and/or from the study:

- Sustained hemoglobin  $\geq$  12 mg/dL (not influenced by transfusions).
- Any toxicity  $\geq$  Grade 3 (Appendix H).
- Adverse event that, in the judgment of the investigator, may cause severe or permanent harm or that rules out continuation of treatment.
- Hypersensitivity reaction to TFP.
- Withdrawal of consent.
- Death.
- Lost to follow-up.
- Pattern of significant noncompliance.

The reason for subject withdrawal must be documented in the subject chart / source records.

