### **8.9.3 Dispensing of Study Drug**

The subject will be dispensed a 21 day supply of 1 mg or 5 mg tablets based on Dose Level 1, 2, or 3 and 4, respectively. The subject will receive study drug once during this study.

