### **8.9.4 Return or Destruction of Study Drug**

At the completion of the study, there will be a final reconciliation of drug shipped, drug consumed and drug remaining. This reconciliation will be logged on the drug reconciliation form, signed and dated. Any discrepancies noted will be investigated, resolved, and documented prior to return or destruction of unused study drug. Drug destroyed on site will be documented in the study files.

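### Compliance is assessed only by subject report and no minimum intake is set, so an under-dosed subject without toxicity counts as toxicity-free at the assigned dose

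*Combined protocol and SAP*

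**What the plan says.** Section 8.5 is the whole compliance plan. The team will "assess compliance with the study treatment by report at each study visit", and "The subject may be discontinued by the study PI at any time for non-compliance with the study treatment regimen". Section 7.6.1 lists "Pattern of significant noncompliance" among the reasons for withdrawal. Neither section gives a threshold.

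On tablets, the Drug Accountability Log in Section 8.4 has an entry for "Number of pills dispensed" and none for tablets returned. Section 8.9.3 says "The subject will receive study drug once during this study", so the full 21-day supply is handed over at Visit 1. Sections 9.3 and 9.4 (Visits 2 and 3) and the Appendix A schedule list no tablet return or count. Section 8.9.4 says: "At the completion of the study, there will be a final reconciliation of drug shipped, drug consumed and drug remaining".

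On the use of the data, Section 3.5.1 holds the interim analysis once three subjects have finished 21 days of treatment, without defining this by doses taken. Section 14.2 puts everyone with one or more doses in the safety analysis. Section 14.3 uses all enrolled subjects for the primary endpoint. No section defines a subject evaluable for toxicity, a minimum intake or a replacement rule.

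**The concern.** Section 3.5 itself states that side effects of TFP depend on dose and plasma level. A subject who takes less drug is then less likely to show toxicity, and under this plan that absence counts in full as evidence that the assigned dose is tolerated. With three or six subjects per decision, one such subject is a third or a sixth of the data. The error has one direction: towards escalating, and towards declaring too high an MTD. That matters because Section 2 says the result will support a later proof-of-concept trial.

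The dosing scheme makes a sincere misreport possible. Under Section 8.2, the 2 mg and 10 mg doses are two tablets of the strength taken singly in the cohort below. Section 7.2, criterion 6, lets a subject from an earlier cohort enter a later one. Someone used to one 5 mg tablet a day could keep to one and truthfully report taking the drug every day. A tablet count would show this; the question may not.

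**Working it through.** **1. The plan's own figure.** Section 14.1 gives 3 to 24 subjects. Four cohorts of at most 6 give 4 × 6 = 24, and stopping in the first cohort gives 3. Both reproduce.

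**2. Tablets per subject** (Section 8.2, 21 days):
- 1 mg and 5 mg cohorts: 1 × 21 = 21 tablets.
- 2 mg and 10 mg cohorts: 2 × 21 = 42 tablets.
- Illustration: one of two 5 mg tablets each day is 5 mg/day, the dose of the cohort below; 21 of the 42 tablets would remain.

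**3. Chance of passing a dose level.** From Section 6.1 (Cohorts C and D), a dose passes on 0/3, or on 1/3 followed by none of the next 3. With true rate p of qualifying toxicity and full intake:

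P = (1−p)³ + 3p(1−p)² × (1−p)³

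At p = 0.30: 0.343 + 0.441 × 0.343 = 0.494.

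Now let m of the first three be exposed, let the others have no drug toxicity, and let the three added subjects take full doses:

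P = (1−p)^m + m·p·(1−p)^(m−1) × (1−p)³

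At p = 0.30, m = 2: 0.490 + 0.420 × 0.343 = 0.634. With m = 1: 0.700 + 0.300 × 0.343 = 0.803.

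A milder case gives one of the first three half the risk (p/2). At p = 0.30 the chance of no event is 0.7 × 0.7 × 0.85 = 0.4165. The chance of exactly one is 2 × 0.3 × 0.7 × 0.85 + 0.49 × 0.15 = 0.4305. So P = 0.4165 + 0.4305 × 0.343 = 0.564. The same steps give the other rows.

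| Assumed true rate | Full intake | One of 3 at half risk | One of 3 takes none | Two of 3 take none |
|---|---|---|---|---|
| 20% | 70.9% | 75.6% | 80.4% | 90.2% |
| 30% | 49.4% | 56.4% | 63.4% | 80.3% |
| 40% | 30.9% | 38.6% | 46.4% | 68.6% |

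The toxicity rates, the number of under-dosed subjects and their reduced risk are all assumptions; the documents give none of them.

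**4. What a clean cohort shows.** After no events in m exposed subjects, the one-sided 95% upper bound on the toxicity rate is 1 − 0.05^(1/m): 63.2% for m = 3, 77.6% for m = 2, 95.0% for m = 1.

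**5. What a count must allow for.** Visit 3 is Day 22 ± 2. A fully compliant 10 mg subject seen on Day 20 before that day's dose has taken 19 × 2 = 38 tablets and properly holds 4. Dividing by the full supply gives 38/42 = 90.5%; dividing by doses due gives 38/38 = 100%. The dose holds in Section 3.5.2 (up to 7 days) also leave tablets legitimately.

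**The case against.** Self-report over a short, once-daily course is a disclosed choice, and it is not the only relevant information in the plan. Section 15.6 gives the medical monitor summaries of compliance and of treatment given. Appendix I puts drug accountability within monitoring. Sections 7.6.1 and 8.5 allow non-compliant subjects to be removed. Appendix J collects blood to measure drug amount, which is an objective measure of exposure. These are partial safeguards, and they stand as such. None is tied to an escalation decision, removal is discretionary, and the drug level serves exploratory work, with sampling described in Sections 9.2 to 9.4 as done where applicable.

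A second objection is that a count alone changes nothing while every subject stays in the decision. That is right: the count needs an evaluability rule beside it.

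Four stronger readings are tempting, and the documents do not support them.
- A reader might infer that tablets are already reconciled by count for each subject. Section 8.9.4 names no counting method and no return by subject.
- A reader might infer that reconciliation certainly falls after every escalation decision. That is the likelier reading, since the section also covers drug shipped. But Section 7.5 and Appendix G use the word study for one subject's four weeks, so the timing is not settled. What is clear is that no link to cohort decisions is stated.
- A reader might infer that a count gives doses taken. It shows tablets not returned.
- A reader might infer that the MTD will be too high. Without an adherence figure, only the direction of the bias can be stated.

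**Conclusion.** The point holds as a low-cost improvement to the design. The only compliance method described is subject report, no tablets are requested back during treatment, and no minimum intake is required before a subject counts as toxicity-free. Any under-dosing therefore pushes towards escalation.

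Its size is unknown. At assumed true rates of 20% to 40%, one non-taker among the first three raises the chance of passing a dose by 9.5 to 15.5 percentage points (70.9% to 80.4%; 30.9% to 46.4%). One subject at half risk raises it by 4.7 to 7.7 points. The non-taker figures are extreme, because they assume no drug toxicity at all in that subject; partial under-dosing has a smaller effect in the same direction. None of these figures is a forecast for this trial.

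**What to change.** - In Section 8.5 and Appendix A, ask subjects to bring the container to Visits 2 and 3. Count the tablets, and return the container at Visit 2, since drug is dispensed once.
- Add a returned-tablets field to the Drug Accountability Log in Section 8.4.
- Compute percent of scheduled doses taken as (tablets dispensed − tablets returned) ÷ (tablets per day × dosing days due up to the actual visit, less days held under the protocol). Show it for each subject at each cohort's interim analysis.
- In Section 14.3, keep every dosed subject in the safety set and count any subject with a qualifying toxicity whatever the tablet count. This keeps in subjects who cut doses because of toxicity.
- State that a toxicity-free subject below a minimum intake, set by the sponsor in advance, does not count as toxicity-free for escalation and is replaced.
- Use Appendix J drug levels as a cross-check where drawn.

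The cost is a few minutes per visit and one more field, plus a protocol amendment for the evaluability and replacement rule. Replacements could take enrolment above 24, so Section 14.1 should restate that maximum as evaluable subjects. Tablets removed but not swallowed would still be missed.
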